10.3 SAFETY ANALYSIS

Not applicable.

Statistical and Epidemiological Analysis Plan (SEAP) for Observational and Non-Interventional Studies (ONIS)

Page 19 of 36

11. QUALITY CONTROL

The study will strictly follow key elements of the Guideline for Good Pharmacoepidemiology Practices (GPP) and other relevant standard operating procedures (SOPs). The study report will be reviewed, approved and archived per BI SOP. Quality control methods during the whole process of data management is described in section 9, and quality control methods for data analyses are summarized below.

One data analyst from will build measures (variables) for cohort inclusion and outcomes. Whenever possible, validated algorithms will be used for variables, to minimize misclassification and information bias. All measures created, cohorts developed, statistical analyses implemented, and tables output will undergo quality control review performed by at least one additional Analyst from Quality controls include checks for the validity and logical content of codes and checks for missing values and variables. In order to control for potential inconsistencies and errors, all variables will be tabulated. The distribution of each variable will be examined.

The ONIS Lead will verify that the data analyst has followed methodology specified in the protocol, as well as any relevant programming SOPs and good programming practices. Documentation of key programming decisions should be evident within the program. The investigator or ONIS Lead will verify that any assumptions made by the data analyst are consistent with expectations.

ANNEX 1. ADDITIONAL INFORMATION

None.

ANNEX 2. MOCK TABLE AND FIGURE

The following figures and tables will be developed for analyses of primary, secondary and exploratory objectives and will be replicated for subgroup analyses and sensitivity analyses, pending feasibility.

Table 1. Patient baseline demographic characteristics for Cohort 1 and Cohort 2

Demographic characteristics	Cohort 1	Cohort 2
Number of patients, N		
Index year, N (%) 2013		
2014		
2015		
2016		
2017		
2018		
2019		
2020		
2021		
Age at initial diagnosis, years		
$Mean \pm SD$		
Median (IQR)		
Min, Max		
Missing / Unknown		
Age (categorized) at initial diagnosis, N (%)		
<65		
≥65		
Missing / Unknown		
Age at index, years		
$Mean \pm SD$		
Median (IQR)		
Min, Max		

Statistical and Epidemiological Analysis Plan (SEAP) for Observational and Non-Interventional Studies (ONIS)

Page 21 of 36

Demographic characteristics	Cohort 1	Cohort 2
Missing / Unknown		
Age (categorized) at index, N (%)		
<65		
≥65		
Missing / Unknown		
Sex, N (%)		
Female		
Male		
Missing / Unknown		
Insurance type, N (%)		
National medical insurance		
Commercial insurance		
Out of pocket		
Others		
Missing / Unknown		
Region, N (%)		
Eastern China		
Central China		
Western China		
Northeast China		
Missing / Unknown		

Abbreviations: N = number; SD = standard deviation; IQR = interquartile range; min = minimum; max = maximum

Notes: Eastern China includes Beijing, Tianjin, Hebei, Shanghai, Jiangsu, Zhejiang, Fujian, Shandong, Guangdong, and Hainan; central China includes Shanxi, Anhui, Jiangxi, Henan, Hubei, and Hunan; western China includes Inner Mongolia, Guangxi, Chongqing, Sichuan, Guizhou, Yunnan, Tibet, Shaanxi, Gansu, Qinghai, Ningxia, and Xinjiang; northeast China includes Liaoning, Jilin, and Heilongjiang.

Statistical and Epidemiological Analysis Plan (SEAP) for Observational and Non-Interventional Studies (ONIS)

Page 22 of 36

Table 2. Patient clinical characteristics for Cohort 1 and Cohort 2

Clinical characteristics	Cohort 1	Cohort 2
Number of patients, N Year of initial diagnosis, N (%)		
Before 2013		
2013		
2014		
2015		
2016		
2017		
2018		
2019		
2020		
2021		
Missing / Unknown		
Disease stage at initial diagnosis, N (%)		
0		
I		
II		
III		
IV		
Missing / Unknown		
Histology, N (%)		
Dedifferentiated		
Other		
Missing / Unknown		
ECOG performance status, N (%)		
0		
1		
2		
3		
4		
Missing / Unknown		

Statistical and Epidemiological Analysis Plan (SEAP) for Observational and Non-Interventional Studies (ONIS)

Page 23 of 36

Clinical characteristics	Cohort 1	Cohort 2
Primary tumor site, N (%)		
Head or neck		
Retroperitoneum or abdomen		
Extremity		
Pelvis		
Thorax or trunk		
Other		
Missing / Unknown		
Presence of metastases, N (%)		
Yes		
No		
Missing / Unknown		
Metastatic site, N (%)		
Adrenal		
Bone		
Brain		
Distant lymph node metastases		
Liver		
Lung		
Other		
Missing / Unknown		
Number of surgeries prior to 1L		
$Mean \pm SD$		
Median (IQR)		
Min, Max		
Missing / Unknown		
Charlson comorbidity index		
$Mean \pm SD$		
Median (IQR)		
Min, Max		
Missing / Unknown		
History of smoking, N (%)		

Statistical and Epidemiological Analysis Plan (SEAP) for Observational and Non-Interventional Studies (ONIS)

Page 24 of 36

Clinical characteristics	Cohort 1	Cohort 2
Never smoker		
Former smoker		
Current smoker		
Missing / Unknown		
$BMI, kg/m^2$		
$Mean \pm SD$		
Median (IQR)		
Min, Max		
Missing / Unknown		

Abbreviations: N = number; SD = standard deviation; IQR = interquartile range; min = minimum; max = maximum; BMI = body mass index (defined as [weight in kilograms] / [height in meters]²); ECOG = Eastern Cooperative Oncology Group; 1L = first line.

Statistical and Epidemiological Analysis Plan (SEAP) for Observational and Non-Interventional Studies (ONIS)

Page 25 of 36

Table 3. Overall survival from index for Cohort 1

At 18 months, [95% CI]

At 24 months, [95% CI]

	Cohort 1	
	N=	
Overall survival from Index, months		
KM Median, [95% CI]		
IQR		
Survival rate at different time point, (100/1000 person years) At 6 months, [95% CI]		
At 12 months, [95% CI]		

Abbreviations: KM= Kaplan–Meier; CI = confidence interval; IQR = interquartile range.

Statistical and Epidemiological Analysis Plan (SEAP) for Observational and Non-Interventional Studies (ONIS)

Page 26 of 36

Table 4. Survival from initial diagnosis for Cohort 1 and Cohort 2

	Cohort 1,	Cohort 2,	
	N =	N=	
Survival from initial diagnosis, months			
KM Median, [95% CI]			
IQR			
Survival rate at different time point, (100/1000 person years) At 6 months, [95% CI]			
At 12 months, [95% CI]			
At 18 months, [95% CI]			
At 24 months, [95% CI]			

Abbreviations: KM= Kaplan–Meier; CI = confidence interval; IQR = interquartile range.

Statistical and Epidemiological Analysis Plan (SEAP) for Observational and Non-Interventional Studies (ONIS)

Page 27 of 36

Table 5.	Number	of total	lines of	f systemic	treatment

	Cohort 1,	Cohort 2,
	N=	N=
Total lines of systemic treatment		
$Mean \pm SD$		
Median (IQR)		
Min, Max		
Missing / Unknown		
Total lines of treatment (categorized), N (%)		
1		
2		
3		
4		
≥5		
Missing / Unknown		

Abbreviations: N = number; SD = standard deviation; IQR = interquartile range; min = minimum; max = maximum.

Statistical and Epidemiological Analysis Plan (SEAP) for Observational and Non-Interventional Studies (ONIS) Page 28 of 36

Table 6. Treatment types for Cohort 1 and Cohort 2 by line of therapy

V 1	Cohort 1,				Cohort 2,		
	N=				N =		
	1L	2L	3L	_	1L	2L	3L

Treated, N (%)

Yes

No

Regimens, N (%)

Doxorubicin

Epirubicin

Liposomal doxorubicin

AD (doxorubicin, dacarbazine)

AIM (doxorubicin, ifosfamide, mesna)

Ifosfamide, epirubicin, mesna

Larotrectinib (NTRK fusion pos sarcomas only)

Entrectinib (NTRK fusion pos sarcomas only)

Pazopanib

Eribulin

Trabectedin

AD LMS only (doxorubicin, dacarbazine)

Gemcitabine and docetaxel

Gemcitabine

Gemcitabine and vinorelbine

Gemcitabine and dacarbazine

Dacarbazine

Ifosfamide

Temozolomide

Vinorelbine

Regorafenib

MAID (mesna, doxorubicin, ifosfamide, dacarbazine)

Statistical and Epidemiological Analysis Plan (SEAP) for Observational and Non-Interventional Studies (ONIS)

Page 29 of 36

	Cohort 1,			Cohort 2,			
		N =			N=		
·	1L 2L 3L		1L	2L	3L		

Pembrolizumab

durvalumab

Other

Concurrent steroid therapy, N (%)

Yes

No

Concurrent immunosuppressant therapy, N (%)

Yes

No

Concurrent hormone replacement therapy, N (%)

Yes

No

Abbreviations: 1L = first line; 2L = second line; 3L = third line.

Notes: Specific treatments and categories are ordered from highest to lowest frequency and may change upon examination of the data.

Statistical and Epidemiological Analysis Plan (SEAP) for Observational and Non-Interventional Studies (ONIS)

Page 30 of 36

Table 7. Time to next treatment	by l	line of	f treatment f	for	Cohort 1	and	Cohort 2
---------------------------------	------	---------	---------------	-----	----------	-----	----------

	Cohort 1,	Cohort 2,
	N =	N=
Treated, N (%)		
Yes		
No		
Time from diagnosis to 1L treatment, months Median, [95% CI]		
IQR		
Fime from 1L treatment to 2L treatment, months Median, [95% CI]		
IQR		
Time from 2L treatment to 3L treatment, months Median, [95% CI]		
IQR		

Abbreviations: CI = confidence interval; IQR = interquartile range; 1L = first line; 2L = second line; 3L = third

Statistical and Epidemiological Analysis Plan (SEAP) for Observational and Non-Interventional Studies (ONIS)

Page 31 of 36

Table 8. Duration	of treatment by	line for	Cohort 1	and Cohort 2

	Cohort 1,	Cohort 2, N=	
	N =		
Treated, N (%)			
Yes			
No			
Duration of 1L treatment, months			
Median, [95% CI]			
IQR			
Duration of 2L treatment, months			
Median, [95% CI]			
IQR			
Duration of 3L treatment, months			
Median, [95% CI]			
IQR			

Abbreviations: CI = confidence interval; IQR = interquartile range; 1L = first line; 2L = second line; 3L = third line.

Statistical and Epidemiological Analysis Plan (SEAP) for Observational and Non-Interventional Studies (ONIS)

Page 32 of 36

Table 9. Healthcare resource utilization for Cohort 1 and Cohort 2

	Cohort 1,	Cohort 2,
	N=	N=
Inpatient admissions		
$Mean \pm SD$		
Median (IQR)		
Min, Max		
Missing / Unknown		
Total days of hospital stay for inpatien $\operatorname{Mean} \pm \operatorname{SD}$	nt admission, days	
Median (IQR)		
Min, Max		
Missing / Unknown		
Average days of hospital stay for each Mean \pm SD	inpatient admission, days	
Median (IQR)		
Min, Max		
Missing / Unknown		
Outpatient visits		
$Mean \pm SD$		
Median (IQR)		
Min, Max		
Missing / Unknown		
Emergency room visits		
$Mean \pm SD$		
Median (IQR)		
Min, Max		
Missing / Unknown		

Abbreviations: SD = standard deviation; IQR = interquartile range; min = minimum; max = maximum

Table 10. Direct medical cost for Cohort 1 and Cohort 2

	Cohort 1,	Cohort 2,
	N =	N=
Total cost of hospitalization, CNY $Mean \pm SD$		
Median (IQR)		
Min, Max		
Missing / Unknown		
Average cost per hospitalization, CNY $Mean \pm SD$		
Median (IQR)		
Min, Max		
Missing / Unknown		
Total cost of outpatient visit, CNY $Mean \pm SD$		
Median (IQR)		
Min, Max		
Missing / Unknown		
Average cost per outpatient visit, CNY $Mean \pm SD$		
Median (IQR)		
Min, Max		
Missing / Unknown		
Total cost of Emergency Room visit, CNY $Mean \pm SD$		
Median (IQR)		
Min, Max		
Missing / Unknown		
Average cost per Emergency Room visit, CNY $\label{eq:mean} \mathbf{Mean} \pm \mathbf{SD}$		
Median (IQR)		
Min, Max		
Missing / Unknown		

Abbreviations: SD = standard deviation; IQR = interquartile range; min = minimum; max = maximum; CNY = Chinese Yuan

Statistical and Epidemiological Analysis Plan (SEAP) for Observational and Non-Interventional Studies (ONIS)

Figure 1. Kaplan-Meier curve of Overall survival for Cohort 1, from index

[figure not shown]
[figure not shown]
[figure not shown]

Figure 2. Kaplan-Meier curve of survival after initial diagnosis for Cohort 1 and Cohort 2, from initial diagnosis

Statistical and Epidemiological Analysis Plan (SEAP) for Observational and Non-Interventional Studies (ONIS)

Figure 3. Kaplan-Meier curve of time to next treatment for Cohort 1 and Cohort 2, from 1L initiation

Statistical and Epidemiological Analysis Plan (SEAP) for Observational and Non-Interventional Studies (ONIS)

Page 36 of 36

Figure 4. Kaplan-Meier curve of duration of treatment for Cohort 1 and Cohort 2, from 1L initiation

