9.7.3. Analysis of exploratory objectives

Patient demographic, clinical characteristics and treatment outcomes will be reported for Cohort 1 and Cohort 2 (See Section 9.3.1.3 for variable definitions). If multiple records for a variable exist during the baseline period, the record closest to index will be chosen. The number of missing values will be reported for each variable, and percentages for categorical variables will be based on non-missing values. Time from diagnosis to 1L treatment, time to next treatment and duration of treatment by LOT will be estimated using KM methods to obtain median estimates with 95% CIs and IQRs.

HCRU including number of visits and days of hospitalization will be summarized as counts (n) and proportions (%). Direct medical cost will be summarized using mean, median and IQR.

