6.4 STUDY VISITS

Definitions of relevant time periods are detailed below.

Study period: January 1, 2013 – December 31, 2022

Baseline period: All available data prior to index date

Cohort identification period: January 1, 2013 – December 31, 2021 (one year before end of study period)

[figure not shown]
Statistical and Epidemiological Analysis Plan (SEAP) for Observational and Non-Interventional Studies (ONIS)

Index date: The index date for Cohort 1 will set to the date of initiation of 1L treatment; the index date for Cohort 2 will be the date of initial DDLPS diagnosis during cohort identification period.

Follow-up period: From index date until date of death, if available, or the date of censoring if there is no record of death, whichever occurs first. For survival and treatment patterns, the date of censoring will be the last activity date, defined as the date of the last visit of any type prior to the end of the study period.

Figure 1 illustrates the time periods for the study timelines.

(a). Cohort 1

(b). Cohort 2

[figure not shown]

Figure 1. Overall study period

Abbreviations: 1L = first line

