10. DATA ANALYSIS

The statistical analysis plan for the study is summarized below. This study will be descriptive in nature.

For continuous variables, they'll be descriptively summarized using the mean with the standard deviation (SD), the median with the interquartile range (IQR), and the maximum and minimum values, as appropriate.

For categorical variables, the numbers and proportions of patients in different categories of the variable will be reported. Missing values will be presented as counts and percentages but excluded from the denominator when calculating proportions, unless there are additional instructions specified.

For time-to-event variables, the number and percentage of patients with events and censoring

Statistical and Epidemiological Analysis Plan (SEAP) for Observational and Non-Interventional Studies (ONIS)

Page 17 of 36

will be summarized. The median survival time and its 95% confidence interval (CI) will be calculated using the Kaplan–Meier (KM) method, and KM plots will be provided.

It is anticipated that sample sizes for variables may vary due to unknown or missing data in the database. The number of patients with missing data for each variable will be summarized and reported. With the exception of the imputation of partial missing date values, no other imputation of missing values will be undertaken; however, the impact of missing data on interpretation of findings will be acknowledged and discussed in the final study report.

For all analyses, data for patients will be censored when lost to follow-up (i.e., still alive as of their last visit prior to end of study period).

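### The visible shells of SAP Tables 9 and 10 give cumulative use and cost with no person-time rate and no follow-up time, so their columns cannot be read side by side

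*SAP*

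**What the plan says.** Protocol 9.7.3 states "HCRU including number of visits and days of hospitalization will be summarized as counts (n) and proportions" and, for cost, "Direct medical cost will be summarized using mean, median and IQR".

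SAP Annex 2 has 11 row blocks across Tables 9 and 10, with one column per cohort and mean, SD, median, IQR, minimum and maximum in each.

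- Seven blocks are cumulative: admissions, total hospital days, outpatient visits, emergency visits, and total cost by setting, such as "Total cost of hospitalization, CNY".
- Four are per-episode averages: days per admission, and cost per hospitalization, outpatient visit and emergency visit.
- None carries a per-month or per-year denominator, and neither table has a follow-up row.

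The Annex says its tables will be repeated for subgroup and sensitivity analyses where feasible.

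SAP 6.4 sets "Study period: January 1, 2013 – December 31, 2022", with index dates up to the end of 2021. Follow-up runs "From index date until date of death, if available, or the date of censoring if there is no record of death, whichever occurs first", and SAP 10 adds that "data for patients will be censored when lost to follow-up". The clock starts at different points: "The index date for Cohort 1 will set to the date of initiation of 1L treatment", whereas Cohort 2 is indexed at initial diagnosis.

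**The concern.** A cumulative total is use per unit of time multiplied by time observed. If observed time differs between two columns, their totals can differ with no difference in intensity of care, or agree despite one. Per-episode averages do not settle this, because they say nothing about how often episodes occur.

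Describing cost and resource use is a stated exploratory objective, and protocol section 12 says the results may supplement regulatory submissions. A reader given two cohort columns, or a main and a pre-COVID column, will compare them, and the tables as drawn offer no means of allowing for follow-up.

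Separately, counts and proportions do not suit numbers of visits or hospital days, and they disagree with the means, SDs and medians in Table 9.

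**Working it through.** The plan states no figure on this point. The survival inputs come from protocol 9.5. As a check on them, a simulated Kaplan-Meier log-log interval with 20% random censoring gave 6.72 to 9.45 months for N = 300 and median 8, against the tabulated 6.732 to 9.435.

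**Inputs**
- Survival T: exponential, median 10 months (protocol 9.5; 8 and 12 are also used there). λ = ln 2 / 10 = 0.0693 per month.
- Index dates: taken as uniform over January 2013 to December 2021. Time C from index to the end of 2022 is then uniform on 12 to 120 months.
- Cohort 2 survival: not in the documents. Assumed medians are 12 to 60 months.

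**Cohort 1 follow-up, F = min(T, C), administrative censoring only**

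P(F > t) = exp(−λt) for t ≤ 12, and exp(−λt) × (120 − t)/108 beyond that.
- Lower quartile: exp(−0.0693 × 4.15) = 0.75, so 4.2 months.
- Upper quartile: exp(−0.0693 × 19.03) × 100.97/108 = 0.267 × 0.935 = 0.25, so 19.0 months.
- 5th and 95th percentiles: 0.7 and 39 months.

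Mean = (1/λ)(1 − q), where q = [exp(−12λ) − exp(−120λ)]/(108λ) = (0.4353 − 0.0002)/7.486 = 0.058. Mean = 14.43 × 0.942 = 13.6 months. The value q is also the share administratively censored, about 6% (4% at median 8, 8% at median 12).

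**Ratio of mean totals, Cohort 2 to Cohort 1, at equal and constant monthly use**

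| Assumed Cohort 2 median (months) | Mean follow-up (months) | Ratio to 13.6 |
|---|---|---|
| 12 | 15.9 | 1.17 |
| 24 | 27.1 | 2.0 |
| 36 | 34.6 | 2.5 |
| 60 | 43.5 | 3.2 |

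With protocol 9.5's censoring of about 20% in Cohort 1, mean follow-up there is 0.8/λ = 11.5 months. Applying the same dropout hazard (0.0138 per month) to Cohort 2 gives 24.7 and 29.5 months at medians of 36 and 60, so the ratios fall to about 2.1 and 2.6.

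**Within Cohort 1**
- By index year, mean follow-up is 14.4 months for 2013 (C from 108 to 120) and 10.2 for 2021 (C from 12 to 24), a ratio of 1.4. Index year stands in here for the year-of-diagnosis subgroup in protocol 9.7.4.
- Ending identification in 2019 (protocol 9.7.5), with follow-up still to the end of 2022, raises the mean from 13.6 to 14.2 months, about 5%. In Cohort 2 the rise is 13% to 15% at assumed medians of 36 to 60.

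**How far follow-up drives an individual total**

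Take monthly cost as independent of F, with between-patient coefficient of variation CV (assumed; not in the documents). The share of variance in totals explained by follow-up is 1.00 at CV 0, 0.66 at CV 0.5, 0.32 at CV 1 and 0.11 at CV 2. With an up-front cost worth 12 months and CV 2 it is 0.05.

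**The case against.** **Withheld text.** Protocol 9.7.3 refers to section 9.3.1.3 for definitions. That section and the SAP text between 10.1.2 and 10.3 are not in the released documents, and a measurement window could be there. The shells also omit timings that are defined elsewhere: Table 5 shows none, although SAP 7.1.2 sets one for number of lines. This stands as a limit on the claim. It does not remove the point, because a window leaves deaths and losses inside it uncorrected. With a 12-month window, taken only as an illustration, 1 − exp(−12λ) = 56% of Cohort 1 would die within it at a 10-month median.

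**Descriptive purpose.** The objective is exploratory and no formal group comparison is planned. In Cohort 1 only 4% to 8% are administratively censored under the protocol's medians, before loss to follow-up, so cost from 1L to death is a usable description. This stands. A reader might infer that the cost objective cannot be interpreted at all, but the documents do not support that.

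**Stronger readings.** A reader might also infer that the totals mainly measure survival time. That depends on cost variability and timing, which the documents do not give; the explained share runs from 0.05 to 1.00. Nor can it be said that the cohorts will differ because of follow-up. Stage, surgery and systemic treatment differ too, and Cohort 2 is defined by not having started 1L, so it can include untreated advanced disease with short survival.

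**Limits of a rate.** Person-month rates still compare different disease phases, and costs clustered near treatment start or death raise the rate in short survivors. This stands, so rates should supplement the totals.

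**Conclusion.** The point holds for the visible shells. They plan cumulative totals and per-episode averages, with neither a person-time rate nor a follow-up row, while follow-up varies about 4.5-fold between quartiles in Cohort 1 (19.0/4.2) and starts at a different disease milestone in each cohort. Totals are mixed with observation time, and cohort, subgroup and sensitivity columns should not be read against each other as they stand.

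The Cohort 1 figures rest on exponential survival with a 10-month median, uniform index dates and no loss to follow-up. The between-cohort size is unknown. The range from about 1.2-fold to 3.2-fold is illustrative, depends on an assumed Cohort 2 survival and equal monthly use, and narrows with dropout.

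The mismatch between protocol 9.7.3 and Table 9 needs no assumption. SAP section 10 already prescribes means, SDs, medians and IQRs for continuous variables, so the protocol sentence is the one out of line. For an exploratory objective this is a reporting improvement worth making, not a threat to the primary analysis.

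**What to change.** Keep every planned total and per-episode row. Add to Tables 9 and 10:

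1. Follow-up time by column: median, IQR and total person-months.
2. For each total, a per-patient-month rate: the sum of events or CNY divided by the sum of person-months from index to death or last activity, or within the defined window if there is one. Give a 95% CI by bootstrap over patients. The ratio of sums limits the instability that very short follow-up causes in individual rates.
3. n (%) of patients with at least one admission, outpatient visit or emergency visit. Counts and proportions are suitable here.

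Reword protocol 9.7.3 so that visits and hospital days are summarised by mean, SD, median and IQR, as in Table 9. Add a footnote that the rates cover different disease phases in the two cohorts and can be raised by costs near treatment start or death, so they do not make the cohorts fully comparable.

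The cost is a few rows per table and a bootstrap step, using dates and costs that the planned analyses already need.
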